In CA184024, any irAEs occurred in 76% of subjects treated with ipilimumab (10mg/kg) + DTIC, Grade 3 events were reported in 31.6% and Grade 4 events in 10.1%. Treatment-related SAEs were reported for 47% and 6.8% in the ipilimumab plus DTIC and DTIC monotherapy groups respectively. The most common events in the ipilimumab plus DTIC group were increased ALT and AST (19% each). Other SAEs reported in $\geq 5\%$ of subjects in the ipilimumab plus DTIC group included diarrhea (6.5%) and pyrexia (5.7%). There were no treatment-related AEs with an outcome of death in the ipilimumab plus DTIC group and 1 (0.4%) in the DTIC group (GI hemorrhage). In a pooled analysis of 325 patients receiving 10mg/kg ipilimumab therapy, AEs (any grade) were reported in 96.9%, Grade 3-4 AEs in 37.5%, related AEs in 84.3%, Grade 3-4 related AEs in 30.5%, SAEs in 51.7%, related SAEs in 29.2%.

In CA184022, 3 dose levels of ipilimumab were studied, including 0.3 (n=72) vs 3 (n=71) vs 10mg/kg (n=71). Overall irAEs were reported in 64.8% and 70.4% of patients treated at 3mg/kg and 10mg/kg respectively, Grade 3-4 irAEs were reported in 7% and 25.4% respectively, GI irAEs in 32.4% and 39.4% respectively, Grade 3-4 GI irAEs in 2.8% and 15.5% respectively, hepatic grade 3-4 irAEs in 0% and 2.8% respectively, endocrine Grade 3-4 irAEs in 2.8% and 1.4% respectively and skin Grade 3-4 irAEs in 1.4% and 4.2% respectively.

In summary, the safety profile of ipilimumab 10mg/kg remains consistent with the low-dose safety profile in that most of the treatment-related SAEs are characteristic of immune-related toxicity, and most of the IRAEs are reported in the GI, hepatic and endocrine systems. However, the frequency of IRAEs, particularly of high grade events, is higher with 10mg/kg of ipilimumab at multiple doses compared with the IRAE frequency reported for lower doses.

5.1.11. Drug Related Deaths:

Based on the data available in the BMS internal safety database as of 24-June-2011, study-drug related deaths based on the investigator's assessment were reported in 82 subjects. Therefore, the reported rate of treatment-related deaths from the program-wide studies was approximately 0.8% (82/10,000). While a causal role of ipilimumab in these 82 deaths could not be ruled out, confounding factors could be identified in most of these cases.

5.1.12. Clinical Efficacy:

Ipilimumab prolonged survival in subjects with pre-treated and previously untreated advanced melanoma, based on results from 2 large, multinational, double-blind, Phase 3 studies (MDX010-20 and CA184024), supported by data from Phase 2 studies.

In prostate cancer, ipilimumab is being evaluated in Phase 1 and 2 studies, as well as in a randomized Phase 3 trial. Although sample sizes were small, response as measured by $\geq 50\%$ decline in PSA have been reported. Responses were durable, ranging between 2 and 24 months.

5.1.13. Association between Safety (IRAEs) and Efficacy (OS)

Results from MDX010-20 suggested a tendency for improved OS in subjects with any IRAEs. In CA184024, analyses using the Cox proportional hazards model were conducted to assess the association of IRAEs and OS. Overall, the results showed a significant improvement in OS in subjects with Grade 3/4 IRAEs (any Grade 3/4: HR 0.23 [95% CI: 0.10, 0.54]; liver Grade 3/4: HR 0.25 [95% CI: 0.10, 0.65])(27). These results should be interpreted with caution, as the analysis was not adjusted for other prognostic factors.

Based on the current clinical experience with the use of corticosteroids for the management of treatment-emergent IRAEs, corticosteroids do not adversely affect the antitumor response in subjects with objective responses and concomitant serious IRAEs(28)

5.1.14. Formulation

The Ipilimumab injection, 200 mg/40 mL (5 mg/mL), is formulated as a clear to slightly opalescent, colorless to pale yellow, sterile, nonpyrogenic, single-use, isotonic aqueous solution that may contain particles. The ipilimumab injection, 200 mg/40 mL, is supplied in 50-cc type I flint glass vials, respectively, stoppered with gray butyl stoppers and sealed with aluminum seals. The drug product is formulated at a concentration of 5 mg/mL at a pH of 7.0. The quantitative composition for the 50- and 200-mg/vial products is provided in Table 1.

Table 1. Quantitative Composition of Ipilimumab Injection

Component	Process B		Process C/C.1	
	50 mg/vial ^a	200 mg/vial ^b	50 mg/vial ^a	200 mg/vial ^b
Ipilimumab	53.5 mg	213.0 mg	53.5 mg	213.0 mg
Sodium Chloride	62.6 mg	249.0 mg	62.6 mg	249.0 mg
TRIS Hydrochloride	33.7 mg	134.3 mg	33.7 mg	134.3 mg
Pentacetic Acid ^c	0.42 mg	1.67 mg	0.42 mg	1.67 mg
Mannitol	107 mg	426 mg	107 mg	426 mg
Polysorbate 80	1.07 mg	4.26 mg	1.18 mg	4.69 mg
Sodium Hydroxide		QS to pH 7.0		
Hydrochloric Acid		QS to pH 7.0		
Water for Injection	QS to 10.7 mL	QS to 42.6 mL	QS to 10.7 mL	QS to 42.6 mL
Nitrogen ^d		Processing Agent		

a Includes a 0.7-mL overfill for vial-needle-syringe withdrawal losses.

b Includes a 2.6-mL overfill for vial-needle-syringe withdrawal losses.

c Diethylenetriaminepentaacetic acid.

d Nitrogen is used to transfer the bulk solution through the prefilter and sterilizing filters into the aseptic area.
Abbreviations: QS = quantity sufficient

5.1.15. Packaging and labeling

Ipilimumab available at a concentration of 5 mg/mL, in single use vials, containing 40 mL (NDC 0003-2328-22) solution.

5.1.16. Storage, handling and dispensing of Ipilimumab

Ipilimumab injection, 50 mg/10 mL (5 mg/mL) or 200 mg/40 mL (5 mg/mL), must be stored refrigerated (2°C to 8°C) and protected from light. Ipilimumab injection must not be frozen. Partially used vials or empty vials of ipilimumab injection should be discarded at the site according to appropriate drug disposal procedures.

Ipilimumab injection may be stored undiluted (5 mg/mL) or following dilution in 0.9% Sodium

Chloride Injection, USP or 5% Dextrose Injection, USP in PVC, non-PVC/non-DEHP, or glass containers for up to 24 hours at 2°C to 8°C or room temperature/room light.

Recommended safety measures for preparation and handling include protective clothing, gloves, and safety cabinets.

Ipilimumab injection (5 mg/mL) can be used for intravenous (IV) administration without dilution after transferring to a polyvinyl chloride (PVC), non PVC/non di (2 ethylhexyl)phthalate (DEHP), or glass container and is stable for 24 hours at 2°C to 8°C or room temperature/room light.

Ipilimumab injection may be diluted in 0.9% Sodium Chloride Injection, United States

Pharmacopeia (USP) or 5% Dextrose Injection, USP to concentrations between 1 mg/mL and 4 mg/mL and stored in PVC, non PVC/non DEHP, or glass containers for up to 24 hours at 2°C to 8°C or room temperature/room light. The product may be infused using a volumetric pump at the protocol-specific dose(s) and rate(s) through a PVC IV solution infusion set with an in-line, sterile, nonpyrogenic, low protein binding filter (pore size of 0.2 μ m to 1.2 μ m). Ipilimumab injection must not be administered as an IV push or bolus injection. Care must be taken to assure sterility of the prepared solutions since the drug product does not contain any antimicrobial preservatives or bacteriostatic agents.

5.1.17. Dose Calculations

- Total dose should be calculated as follows:
- Subject body weight in kg \times 3 mg = total dose, mg Total infusion volume should be calculated as follows:

Total dose in mg \div 5 mg/mL = infusion volume, mL

- Rate of infusion should be calculated as follows:

Infusion volume in mL \div 90 minutes = rate of infusion, mL/min

For example, a patient weighing 114 kg (250 lb) planned to receive 3 mg/kg of the study drug would be administered 342 mg of ipilimumab (114 kg \times 3 mg/kg = 342 mg) with an infusion volume of 68.4 mL (342 mg \div 5 mg/mL = 68.4 mL) at a rate of approximately 0.8 mL/min (68.4 mL \div 90 minutes) in 90 minutes.

5.1.18. Withholding dose due to toxicities likely attributable to Ipilimumab:

Doses may be “withheld” for 21 days from the date when the dose was scheduled after which time the decision must be made by the principle investigator whether to withhold for an additional 21 days (see criteria below), withdraw the patient from the study, or to continue with the next cycle: *Example: it may be necessary to withhold (maximum 21 days) an ipilimumab dose for the following adverse event(s) considered related to ipilimumab:*

Any Grade 2 non-skin related adverse event except for laboratory abnormalities

Any \geq Grade 3 laboratory abnormality.

It is necessary to withhold (maximum 21 days) ipilimumab dosing for the following adverse events:

Any \geq Grade 3 skin-related adverse event regardless of causality;

Any adverse event, laboratory abnormality or intercurrent illness which, in the judgment of the investigator, warrants withholding the dose of study medication.

A dose withholding longer than 21 days after the scheduled dose will lead to permanent discontinuation.

5.1.19. Criteria to resume Ipilimumab therapy addressed:

When the adverse event(s) resolve(s) to Grade 1 or baseline value, and for endocrinopathies which are controlled with chronic therapy:

Restart dosing at the next scheduled time point per protocol.

If the adverse event has not resolved in the protocol-specified dosing window (ie, 3 weeks from last dose \pm 2 days), the next scheduled dose will be withheld.

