5.2.10 Dose Calculations

BMS-986156 dose as determined in group 1.

- If dose was determined to be 100 mg, then it will be infused undiluted at a concentration of 10mg/mL using 10 mL as infusion volume.
- If dose was determined to be 30 mg, then, 3mL should be extracted from the vial containing BMS-986156 at a 10mg/mL concentration and transferred to a sterile and compatible container (vial #2). Then, 7 mL of 0.9% sodium chloride injection or 5% dextrose injection will be added to vial #2 as diluent to achieve a volume of 10mL.

A volume of 10mL, independent of dose determined in group 1, will be infused over 60 min at a rate of 0.167mL/min.

5.3. *Nivolumab (OpdivoTM): manufactured by Bristol-Myers Squibb Co (BMS)*

5.3.1 Physical/Chemical Properties:

Nivolumab, also referred to as BMS-936558-01 or BMS-936558, is a soluble protein consisting of 4 polypeptide chains, which include 2 identical heavy chains and 2 identical light chains with a molecular weight of 146,221 daltons. nivolumab is a clear to opalescent, colorless to pale yellow liquid, with few particulates maybe present and a pH of 5.5 to 6.5.

5.3.2 Mechanism of action:

Nivolumab (also referred to as BMS-936558 or MDX1106) is a human monoclonal antibody (HuMAb; immunoglobulin G4 [IgG4]-S228P) that targets the programmed death-1 (PD-1) cluster of differentiation 279 (CD279) cell surface membrane receptor. PD-1 is a negative regulatory molecule expressed by activated T and B lymphocytes.1 Binding of PD-1 to its ligands, programmed death-ligands 1 (PD-L1) and 2 (PD-L2), results in the down-regulation of lymphocyte activation. Inhibition of the interaction between PD-1 and its ligands promotes immune responses and antigen-specific T-cell responses to both foreign antigens as well as self-antigens. Nivolumab is expressed in Chinese hamster ovary (CHO) cells and is produced using standard mammalian cell cultivation and chromatographic purification technologies. The clinical study product is a sterile solution for parenteral administration.

OPDIVO™ (nivolumab) is approved for use in multiple countries including the United States (US, Dec-2014), the European Union (EU, Jun-2015), and Japan (Jul-2014).

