Prior to starting each treatment cycle, patients will arrive at the Clinical Center for Targeted Therapy or Thoracic Medical Oncology Clinic and undergo safety assessments. In all groups, safety will be assessed by physical examination, observation and adverse experiences, and monitoring clinical chemistry and hematology. Disease progression will be based upon the irRC Criteria. All patients will be evaluated for toxicity upon their first receipt of the trial drug(s) and for therapy response after receiving at least 2 doses of drugs and at least half the scheduled radiation doses.

7.1.1 Dose escalation / de-escalation of BMS-986156 when combined with ipilimumab based on a (3+3) design to determine MTD

Ipilimumab (Yervoy™)

Ipilimumab (3 mg/kg) will be administered as a single 90 minute (+/- 15 minutes) intravenous infusion on the first day of each cycle, every 21 days (\pm 3d).

BMS-986156

BMS-986156 (30 mg or 100 mg) will be given as a single 60 min (+/- 15 minutes) intravenous infusion on the first day of each cycle (\pm 3d). When given in combination with Ipilimumab, BMS-986156 will be given every 21 days (\pm 3d).

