7.1.1.2 Group 2: Dose De-Escalation of BMS-986156 when combined with ipilimumab plus SBRT

BMS-986156 dose as determined in group 1, for combination treatment with ipilimumab, before adding SBRT to the treatment regimen.

Treatment group 2: A modified 3+3 dose de-escalation then expansion to a total of 20 patients will occur at the MTD.

The first 3 subjects will be enrolled at dose level 1 (3 mg/kg ipilimumab + BMS-986156).

- If 0 out of these 3 patients have a DLT, 3 additional patients will then be enrolled on this same dose level.
- If 1 of 3 subjects have a DLT, 3 more patients will then be enrolled at this dose level. If only 1 of the 6 total subjects at dose level has a DLT, then this dose level will be considered safe and all other patient in this arm will be treated at this dose level.
- If 2 of 6 subject have DLT at dose level 1, then the dose will be de-escalated as per table below.
- If 2 of 3 subjects have a DLT at dose level 1, then the dose will be de-escalated as per table below

Dose De-Escalation of Ipilimumab when combining with BMS-986156 plus SBRT.

If MTD from group 1 finds the 30mg BMS-986156 then:

Dose Level 1 3 mg/kg Ipilimumab + 30 mg BMS-986156

Dose Level -1 1 mg/kg Ipilimumab + 30 mg BMS-986156

If MTD from group 1 finds the 100mg BMS-986156 then:

Dose Level 1	3 mg/kg Ipilimumab + 100 mg BMS-986156
Dose Level -1	1 mg/kg Ipilimumab + 100 mg BMS-986156
Dose Level -2	1 mg/kg Ipilimumab + 30 mg BMS-986156

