 - If 1 of 3 subjects have a DLT in dose level, 3 more patients will then be enrolled at this dose level. If only 1 of the 6 total subjects at dose level has a DLT, then this dose level will be considered safe and all other patient in this arm will be treated at this dose level.
 - If 2 of 6 subject has DLT then the dose will be de-escalated as per table below.
 - If 2 of 3 subjects have a DLT at dose level 1, then the dose will be de-escalated as per table below

Dose De-Escalation of BMS-986156 when combining with Nivolumab plus SBRT.

Dose Level 1	480mg Nivolumab + 30 mg BMS-986156
---------------------	------------------------------------

Dose Level -1 480mg Nivolumab + 10 mg BMS-986156**7.1.2. Reinduction for all arms**

Reinduction will be allowed for patients in which the treating physician feels there was benefit from the trial treatment. It will consist of repeating the original treatment using the same schedule for each arm. Radiation may be given during reinduction, but is not required. Pending the treating radiation oncologist judgment, additional radiation therapy to a previously non-irradiated lesion can be administered during re-induction. Timing of radiation during reinduction will be at the discretion of treating Radiation Oncologist.

The target lesion for radiation will be chosen by the treating radiation oncologist. The target lesion must not have been previously irradiated. The target lesion does not have to be within the same organ that was initially treated during the initial treatment (e.g. patients who received initial lung lesion irradiation can have liver or a bone lesion irradiated during re-induction). Radiation dose and fraction will be either at the initial dose (50 Gy in 4 fractions or 60 Gy in 10 fractions) or at a lower palliation dose (30 Gy in 10 fractions) and may also be combined with low dose radiation ranging from 200cGy-1000cGy in multiple fractions, at the discretion of the treating radiation oncologist.

Other tumor sites may be treated for palliation concurrently or sequentially if needed at the discretion of the treating radiation oncologist.

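### Sections 5.1.17 and 5.2.10 contradict the dose levels in 7.1.1.2 and 7.1.1.3: read literally, they give 3 to 10 times the listed dose of at least one drug at every de-escalated level.

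*Combined protocol and SAP*

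**What the plan says.** **Ipilimumab.** Section 5.1.17 has one formula, with no term for dose level: "Subject body weight in kg \times 3 mg = total dose, mg". Its worked example is at the same level: "For example, a patient weighing 114 kg (250 lb) planned to receive 3 mg/kg of the study drug would be administered 342 mg". The opening text of section 7.1.1 also gives 3 mg/kg without exception. The group 2 tables in section 7.1.1.2 reduce ipilimumab to 1 mg/kg at level -1, whichever BMS-986156 dose group 1 selects. If that dose was 100 mg, there is also a level -2: "1 mg/kg Ipilimumab + 30 mg BMS-986156".

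**BMS-986156.** Section 5.2.10 opens with "BMS-986156 dose as determined in group 1" and does not limit this to any group. It then describes two preparations. One is "If dose was determined to be 100 mg, then it will be infused undiluted at a concentration of 10mg/mL using 10 mL as infusion volume"; the other draws 3 mL of drug and adds 7 mL of diluent for 30 mg. It closes: "A volume of 10mL, independent of dose determined in group 1, will be infused over 60 min". Section 7.1.1.3 sets group 3 at 30 mg regardless of group 1, with level -1 as "480mg Nivolumab + 10 mg BMS-986156". The Treatment Scheme (section 1) opens group 3 together with group 1.

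**Link between the sections.** Section 7.1 says that the ipilimumab dose (groups 1 and 2) and the BMS-986156 dose (group 3) will change with the DLT outcome. The calculation sections do not reflect this. The protocol states no order of precedence between sections 5 and 7.

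**The concern.** A dose-calculation section should return the assigned dose for every group and level that the design allows. These two return it only at the starting levels and, for group 3, only if group 1 happens to select 30 mg.

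The mismatch matters most after dose-limiting toxicities have triggered a step down. If the preparation followed section 5, patients at the lower level would receive the dose that the step was meant to move away from. DLTs would then be counted against a level that had not been given. The first primary objective is a safe BMS-986156 dose with ipilimumab, and the others are the safety profiles of the combinations with SBRT. Each depends on the dose given being the dose recorded.

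**Working it through.** **Inputs.** Ipilimumab formula, 5 mg/mL concentration and 90-minute infusion: section 5.1.17. BMS-986156 preparations and rate: section 5.2.10. Listed dose levels: sections 7.1.1.2 and 7.1.1.3.

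**The plan's own figures reproduce.**
- Ipilimumab example: 114 kg x 3 mg/kg = 342 mg; 342 / 5 = 68.4 mL; 68.4 / 90 = 0.76 mL/min, printed as about 0.8.
- BMS-986156: 10 mL / 60 min = 0.167 mL/min; 3 mL x 10 mg/mL = 30 mg, made up to 10 mL.

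The arithmetic inside each section is correct. The conflict is with the levels elsewhere.

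**Same ipilimumab example at the 1 mg/kg level.** 114 x 1 = 114 mg; 114 / 5 = 22.8 mL; 22.8 / 90 = 0.25 mL/min. The printed formula still returns 342 mg, and 342 / 114 = 3.0. The ratio does not depend on weight.

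**Ratio = dose from section 5 taken literally / dose listed in section 7.1.1.**

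| Group and level | Group 1 selects | Ipilimumab | BMS-986156 |
|---|---|---|---|
| Group 2, level 1 | 30 or 100 mg | 3/3 = 1.0 | 1.0 |
| Group 2, level -1 | 30 or 100 mg | 3/1 = 3.0 | 1.0 |
| Group 2, level -2 | 100 mg only | 3/1 = 3.0 | 100/30 = 3.3 |
| Group 3, level 1 | 30 mg | not given | 30/30 = 1.0 |
| Group 3, level 1 | 100 mg | not given | 100/30 = 3.3 |
| Group 3, level -1 | 30 mg | not given | 30/10 = 3.0 |
| Group 3, level -1 | 100 mg | not given | 100/10 = 10.0 |

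At every de-escalated level at least one drug is off by a factor of 3 or more. Group 2 level -1 affects ipilimumab alone. The factor of 10 arises in one cell, which needs both a 100 mg selection in group 1 and de-escalation in group 3. Before group 1 has produced a dose, section 5.2.10 gives no dose at all for the group 3 patients already enrolling.

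**The case against.** The strongest reply is that section 5 is drug information and section 7 is the treatment plan. Section 7.1 says that doses will be modified, the 7.1.1 tables print each level, and group 3's 30 mg starting dose is repeated in many places. Section 5 also defers: 5.1.16 and 5.2.9 refer to the doses the protocol specifies, and 5.2.9 leaves BMS-986156 dilution and administration details to a pharmacy manual. The worked ipilimumab example is explicitly for a 3 mg/kg patient. Section 10 requires IND Office approval before dose levels change.

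Much of this stands. It makes the risk conditional: someone would have to use section 5 as printed and overlook the assigned level. The manual is not among the documents, so what a pharmacy would actually prepare cannot be established. It does not remove the contradiction. References to protocol-specified doses lead back to a protocol whose calculation sections are 5.1.17 and 5.2.10. The deferral to the manual is for BMS-986156 and does not cover ipilimumab. The example is qualified, but the formula above it is not. IND Office approval governs the decision to change level, not the calculation used afterwards.

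Three stronger readings are tempting and not supported:
- A reader might infer that group 3 is always over-dosed. It is not: at level 1 with a 30 mg group 1 result the ratio is 1.0.
- A reader might treat the missing 10 mg preparation as an instruction to give more. By itself it is a gap. Section 5.2.9 permits dilution to 0.1 mg/mL, and 10 mg in 10 mL is 1 mg/mL. The 3-fold and 10-fold figures come from applying the group 1 dose to group 3, not from the missing recipe.
- A reader might fault section 7.1.1 for "BMS-986156 (30 mg or 100 mg) will be given as a single 60 min". Under its heading, which concerns the ipilimumab combination, that is correct: 10 mg is listed only with nivolumab.

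**Conclusion.** The point holds as an internal inconsistency. Section 5.1.17 does not cover the 1 mg/kg levels. Section 5.2.10 does not cover group 3's 10 mg level and does not exempt group 3 from the group 1 dose.

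The size is 3.0-fold for ipilimumab at group 2 levels -1 and -2. For BMS-986156 it is 3.3-fold at group 2 level -2, 1.0 or 3.3 at group 3 level 1, and 3 or 10 at group 3 level -1, according to whether group 1 selects 30 or 100 mg where both are possible.

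These multiples assume literal use of section 5, together with de-escalation or (for group 3 level 1) a 100 mg selection. They describe what the text yields. They do not predict that patients would be over-dosed, because section 7 states the assigned doses and the pharmacy manual has not been seen. Whether section 5 or section 7 carries the intended doses is not decided here.

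**What to change.** Reconcile sections 5.1.17 and 5.2.10, and the unqualified 3 mg/kg statement in section 7.1.1, with the dose-level tables in 7.1.1.1 to 7.1.1.3. The calculation text and the tables should give the same dose for every group and level, and 5.2.10 should say which groups it applies to. A simple test is to repeat the ratio table above on the revised text: every entry should be 1.0. The sponsor and investigators must decide which passages are changed.

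The cost is protocol wording, plus a check of the pharmacy manual against the reconciled text. Whether the manual needs changing cannot be told from the documents. Sample size and analyses are unaffected.

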7.3. Duration of Therapy and Criteria for Treatment Delay

7.3.1. Duration of Therapy:

In the absence withholding treatment cycles due to adverse events, study treatment will be continued for the full 4 Ipilimumab/BMS-986156 cycles, followed by 26 cycles of Nivolumab (group 1 and 2). Nivolumab/BMS-986156 will be given for 4 cycles, followed by 22 cycles of Nivolumab (group3). Nivolumab will be given for a total of 26 cycles on all groups.

7.3.2. Criteria for Treatment Delay:

Patients will delay treatment with ipilimumab/BMS-986156 or nivolumab/BMS-986156 if they experience at least one of the following adverse events considered by the Investigator to be “possibly”, “probably” or “certainly” related to trial drug treatment with or without SBRT treatment:

- Any Grade 3 non-skin related adverse event (excluding alopecia, and Grade 3 nausea, vomiting, and diarrhea for which adequate supportive therapy has been instituted)
- Any Grade 3 skin-related adverse event (including irAEs)
- Any of the Grade 4 hematologic adverse events for >7 days
- Grade 3 fatigue only if ≥ 7 days
- SBRT scheduling conflicts or machine maintenance issues

7.3.3. Criteria for Restart of Ipilimumab/BMS-986156 or nivolumab/BMS-986156 Treatments:

Patients requiring delay or cessation of treatments of trial drugs based on the judgment of the attending physician can be restarted as long as:

- The adverse event is not listed in 7.2.1, and:

- If the adverse event has resolved to \leq Grade 1 severity or returns to baseline within 4 weeks (28 days) of dose administration, treatment will be restarted \geq 4 weeks from the last dose administration, to complete dosing regimen outlined above.
- If the adverse event has not resolved to \leq Grade 1 severity or returned to baseline in the protocol-specified dosing window (3 weeks, for ipilimumab/BMS-986156; 4 weeks for nivolumab/BMS-986156), the next scheduled dose will be omitted and remaining doses will be administered if approved by the Principal Investigator.
- For ipilimumab/BMS-986156: Treatment delays for reasons other than adverse events (e.g. for scheduling conflicts or SBRT machine maintenance issues) are allowed as long as all four 3 week cycle ipilimumab/BMS-986156 doses are given within 8 months. In this scenario, all 4 doses should be administered separated by a minimum interval of 3 weeks.

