7.3.4. Criteria for Permanent Discontinuation of Ipilimumab/BMS-986156 or nivolumab/BMS-986156

Patients who demonstrate signs of progression of disease prior to completion of Ipilimumab/BMS-986156 or Nivolumab/BMS-986156 may continue on trial if determined to provide clinical benefit per the treating physicians and/or PI's discretion.

- Patients will continue to be monitored with visits or phone calls (if patient is unable to arrive) as discussed in section 9.1.3 but will no longer receive further treatment if:
- Patients suffer any of the following adverse events with at least a possible, probable or definite attribution to study treatments:*Adverse event(s) considered related to study treatments as described below:*
 - Any \geq Grade 2 eye pain or reduction of visual acuity that does not respond to topical therapy and does not improve to Grade 1 severity within 2 weeks of starting therapy OR requires systemic treatment;
 - Any \geq Grade 3 bronchospasm or other hypersensitivity reaction;
 - Any other \geq Grade 3 non-skin related adverse event with the exception of laboratory abnormalities;
 - Any Grade 4 laboratory abnormalities, except AST, ALT, or total bilirubin;
 - AST or ALT \geq 8 \times ULN,
 - Total bilirubin \geq 5 \times ULN;
 - Any other Grade 4 adverse event;
 - Drug related toxicity that prevents administration of ipilimumab/BMS-986156 for \geq 21 days or nivolumab/BMS-986156 for 14 days from the scheduled dose
- Any adverse event, laboratory abnormality or intercurrent illness which, in the judgment of the investigator, presents a substantial clinical risk to the subject with continued study drug dosing;
- Subject experiences an allergic/infusion reaction while receiving study drug at a slower infusion rate due to a prior allergic/infusion reaction;
- Any motor neurologic toxicity \geq Grade 3 regardless of causality;

- Any \geq Grade 3 treatment-related sensory neurologic toxicity.
- Drug related toxicity that prevents administration of ipilimumab for \geq 21 days from the scheduled dose

Exceptions to Permanent Discontinuation of ipilimumab dosing:

- Hospitalization for \leq Grade 2 adverse events where the primary reason for hospitalization is to expedite the clinical work-up;

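### Sections 5.1.18-5.1.19 restart ipilimumab after a resolved, related Grade 4 skin event, although section 7.3.4 says that event must end treatment

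*Combined protocol and SAP*

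**What the plan says.** The ipilimumab drug section has its own hold and restart rules.

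- Section 5.1.18 makes a hold mandatory, for at most 21 days, for any event at or above "Grade 3 skin-related adverse event regardless of causality". The text carries a greater-than-or-equal sign before the grade and sets no upper grade.
- The same section adds: "A dose withholding longer than 21 days after the scheduled dose will lead to permanent discontinuation".
- Section 5.1.19 gives the restart condition, "When the adverse event(s) resolve(s) to Grade 1 or baseline value", and the action, "Restart dosing at the next scheduled time point per protocol". It does not ask how severe the event was at its worst or whether it was drug-related.

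The treatment plan in section 7 has a parallel set of rules.

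- Section 7.3.2 delays treatment for "Any Grade 3 skin-related adverse event (including irAEs"), here without the greater-than-or-equal sign.
- Section 7.3.3 allows restart only on the condition that "The adverse event is not listed in 7.2.1", among other requirements.
- Section 7.3.4 gives no further treatment after any event on its list "with at least a possible, probable or definite attribution to study treatments". That list includes "Any other Grade 4 adverse event". The only carve-out for skin sits in a different bullet of 7.3.4, the one for Grade 3 or higher events.

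**The concern.** A clinician facing a resolved Grade 4 skin reaction finds two instructions. The ipilimumab section reads as complete in itself: it has a trigger, a time limit, a restart rule and its own route to permanent discontinuation. Followed as written, it re-doses the patient. Section 7.3.4 says the same patient receives nothing further if the event is at least possibly related. The two places do not refer to each other, and no precedence is stated.

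The stake is re-exposure after a serious skin reaction. Section 5.1.8 notes that fatal toxic epidermal necrolysis has occurred with ipilimumab, and section 3.3 states that no clinical safety data exist for ipilimumab combined with BMS-986156. How such patients are handled also bears on the safety profile that groups 1 and 2 are meant to establish.

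**Working it through.** The plan gives no figure to reproduce, so the check compares the rules case by case.

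1. **Grade 3 skin event, resolved within the hold.** Sections 5.1.18-5.1.19 hold and restart. Section 7.3.2 delays, and 7.3.4 does not stop treatment on grade alone, because its Grade 3 or higher bullet excludes skin. No conflict with 7.3.4.
2. **Grade 4 skin event, at least possibly related, resolved within the hold, dose still due.** Sections 5.1.18-5.1.19 restart. Section 7.3.4 stops permanently. **Conflict.**
3. **Grade 4 skin event, unrelated, resolved within the hold.** Sections 5.1.18-5.1.19 restart. The attribution-based list in 7.3.4 does not apply. No conflict with that list.
4. **Any of these held beyond the limit.** Section 5.1.18 discontinues, and for related events 7.3.4 does too. No conflict.

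Only case 2 fails. The single exception written into 7.3.4, a hospitalization to speed the work-up of an event of Grade 2 or lower, does not reach it.

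**Patients exposed.** Group 1 plus group 2: 20 + 20 = 40. This is a maximum, since group 1 may not fill both dose levels.

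**Length of the permitted hold.** Cycles are 21 days. With a hold of up to 21 days after the scheduled dose, the time from onset to the end of the hold runs from 0 + 21 = 21 days (onset just before a dose is due) to 21 + 21 = 42 days (onset just after a dose). But 5.1.18 also lets the principal investigator extend the hold by another 21 days, which would give 21 + 21 = 42 to 42 + 21 = 63 days. That option contradicts the rule in the same section that a hold beyond 21 days ends treatment, so the window is uncertain.

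**Time to resolution.** Section 5.1.9 gives a median of 4 to 8 weeks for Grade 3-4 immune-related events of all kinds: 4 x 7 = 28 to 8 x 7 = 56 days. Applying this to Grade 4 skin events would be an assumption. Set against 21-42 or 42-63 days, it does not show what share would resolve in time.

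**The case against.** The best defence is that the rules can be read together. A hold and a permanent stop are different actions: a Grade 4 skin event is held at once, then treatment ends if the event is judged related. The open-ended trigger in 5.1.18 is useful because unrelated Grade 4 skin events also need a hold. Section 7 is the treatment plan, while section 5 is drug information. Because 5.1.18-5.1.19 say nothing about BMS-986156, a clinician giving the combination would have to consult section 7 anyway. There are other safeguards: a physician evaluation before each dose (8.2.1), a stop for substantial clinical risk (7.3.4) and removal for unacceptable toxicity (7.3.5).

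Much of this stands, and it lowers the practical risk. It explains the hold but not the restart: 5.1.19 tells the reader to resume dosing and attaches no condition from 7.3.4. Its closing reference to the protocol qualifies the time point and does not bring in the discontinuation criteria. The pointer to section 7.3 in section 3.1.1 concerns stopping the trial, not one patient's dosing. The readable note to the skin algorithm in Appendix B stops therapy for diagnosed SJS or TEN, which is narrower than Grade 4 skin toxicity. The figure itself is not shown, and nothing here rests on it.

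Two stronger readings are tempting, and neither is supported.

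- A reader might infer that section 7 is itself undecided about a Grade 4 rash that improves. Section 7.2.1 lists Grade 3/4 rash only if it fails to settle after a delay of 1-2 weeks, so the restart condition in 7.3.3 is unclear for that event. But 7.3.3 only permits restart, whereas 7.3.4 is mandatory and has no rash exception. Section 7 as a whole stops treatment.
- A reader might infer from the medians in 5.1.9 that many events would not resolve in time, or multiply the 0.8-2.4% skin rate in 5.1.8 by 40. The uncertain hold window rules out the former. The latter rate combines Grades 3 and 4 and is not for this combination, so it neither estimates nor bounds the number of conflicts.

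**Conclusion.** The inconsistency is real and narrow. Sections 5.1.18-5.1.19 are wrong as written for a related Grade 4 skin event that resolves within the hold with a dose still due: they direct a restart that 7.3.4 forbids. The error lies in the drug section, since section 7 needs no interpretation on this point. Few patients, possibly none, of at most 40 would be affected, and the documents do not allow a number to be computed. The conclusion rests on the written rules alone, with no assumption about event rates or resolution times. Priority: a minor safety-consistency correction.

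**What to change.** Keep the hold in 5.1.18 for skin events of Grade 3 or higher, so that unrelated Grade 4 events remain covered. Add to 5.1.19:

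*Restart is subject to 7.3.3 and 7.3.4; ipilimumab/BMS-986156 is permanently discontinued, and not restarted, after any event meeting 7.3.4, including an at least possibly related Grade 4 skin event that has resolved.*

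Optionally, extend the restart condition in 7.3.3 with: *and the event does not meet 7.3.4.* This would also remove any doubt about an improving Grade 4 rash.

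The cost is one short amendment, with no added patients, visits or procedures.
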